# 8. Methods Collection, administration and data analysis

# 8.1 Methods of data collection

A clinical monitor will be assigned to each research center, which will be authorized to monitor, review, procure and ensure that the quality of the information obtained from the participants is reliable and trustworthy. Each monitor will schedule periodic visits to the research centers in order to review the source documents and corroborate the information captured in the case report format (CRF). All clinical monitors will be trained in relation to the information of the study protocol (objective, visits, procedures, range of accepted values, etc.). In the event that the data are not identical between the two registers, the clinical monitor will generate a discrepancy, which must be resolved by the research center in time that the sponsor deems reasonable to meet the objectives of the clinical study. The correction of the discrepancies will be made according to the Good Documentation Practices.

The data registered in the CRF will be reviewed by personnel of Sophia Laboratories, trained in the ophthalmological, clinical and pharmacological area, which will be able to generate discrepancies in the event that the data do not comply with the stipulations of the research protocol or put the participants at risk.

Once all discrepancies generated by the team of clinical monitors and clinical staff have been resolved, the data will be downloaded into an electronic database (Excel Sheet) by personnel designated by the sponsor. A new review of the data will be carried out to corroborate the fidelity of the same and new discrepancies may be generated in case it was considered.

The database generated will be safeguarded by the sponsor and will only have personal access designated by the same.

# 8.1.1 Strategies to complete the follow-up.

- You will be clearly informed of the importance of the study and the benefits that the population will obtain from the results of the study.
- Transportation assistance will be provided in order for the participant to attend their visits.
- Calls, messages or a printed calendar will be made in order to remind the participant of their appointments and the activities that will be carried out, in addition to the estimated duration of the same.
- In case the participant does not attend his appointment, the research center must make a call to know the reason and try to arrange a new appointment within the established window period or an unscheduled appointment.
- In case it is not possible to make an appointment, it will be asked about the presence of adverse events and the reason for leaving the study, such as minimum data.

# 8.2 Data management.

The subject's medical record (including clinical notes, test results, etc.), as well as the subject's diary, and the ICO questionnaire are considered source data.

The IP or the designated person of your team will fill out the Case Report Format (CRF) as well as all other documents provided by the sponsor (for example, documents related to the handling of the treatment).

A CRF was designed to record the data that are required in the protocol and that the researcher collects in each of the visits.

In the case of self-assessment questionnaires, it is not permissible for the principal investigator or person responsible for filling in to modify what was written by the subject of the study.

The data capture in the investigator's site will be done by the investigator or the designated person of his team after performing the Medical File. The researcher or a designated person of your team will be trained in the filling of the CRF

All corrections to the CRF data should be made by the investigator or the designated person of your team in accordance with the instructions provided.

To ensure the confidentiality and security of the data, user names and access codes will be used to restrict access to the system only to authorized personnel.

The monitor must ensure that all the data has been filled in the CRF. After comparing the data against the source documents, the monitor will ask the researcher to make the necessary correction / clarification, so that they are answered and closed as quickly as possible.

The Scientific Committee of Sophia Laboratories, S.A. of C.V. will give the latest medical-scientific review, and will set the standard for freezing the database.

# 8.3 Statistical methodology

#### 8.3.1 Analysis of primary and secondary outcome variables.

The statistical analysis will be carried out by personnel from Sophia Laboratories, S.A. of C.V The statistical program SPSS version 19 (IBM Corporation, Armonk, NY, USA) will be used.

The designated personnel will be blinded to the intervention groups. The coding will be done using consecutive numbers for each intervention group.

The data will be collected and sorted in an excel sheet. Later they will be exported to the platform of the SPSS program. The variables will be categorized according to their nature.

CONFIDENTIAL

The result of the continuous quantitative variables will be presented in measures of central tendency: media, standard deviation and ranges. **See Table 5**. Scales to be used

The normal distribution of the results will be obtained by the Kolmogorov-Smirnov test.

The statistical analysis of the continuous **quantitative variables** to find significant differences (p) will be the following:

- Intra-group analysis: Wilcoxon rank test.
- Inter-group analysis: Kruskal-Wallis test.

The level of difference to consider significance will be an alpha of 0.05 or less.

The result of nominal and ordinal qualitative variables will be presented in frequencies, proportions and percentages. See table 1 (section 6.4.3).

The statistical analysis to identify significant differences of the **qualitative variables** will be done by creating 2x2 contingency tables and will be done as follows:

- • Intra-group difference: McNemar test.
- • Difference between groups: χ2 test (Chi-square) of Pearson.
- The level of difference to consider significance will be of an alpha of 0.05 or less.
- For the reporting of adverse events all eyes of those participants who were randomly assigned to an intervention group after the baseline visit will be considered. The results will be expressed in number of cases (eyes).
- The final report of the results will be shown in tables or graphs, as appropriate.
- It will be considered that the investigational drug is safe and tolerable when there are no clinical and statistical differences in all the variables of primary outcome, with respect to its comparators.
- Those subjects who comply with an adherence greater than 60% will be included in the statistical analysis to meet the objective of the study. It was considered that from the minimum dose necessary to obtain a pharmacological effect and the presence of adverse events (exposure) is sufficient to fulfill the general objective of the design, according to the pharmacological characteristics of the product under investigation.

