#### Statistical methodology:

The data will be expressed with measures of central tendency: mean and standard deviation for the quantitative variables. The qualitative variables will be presented in frequencies and percentages. The statistical analysis will be carried out through the Kruskal-Wallis test for quantitative variables. The difference between the qualitative variables will be analyzed by means of X2 (Chi2). An alpha  $\leq$  0.05 will be considered significant.

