# 5.5.3 Hypothesis

Ha The ophthalmic solution PRO-087 presents a safety and tolerability profile similar to comparators in healthy subjects

*Ho The ophthalmic solution PRO-087 presents a different safety and tolerability profile compared to comparators in healthy subjects.* 

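### For quantitative primary variables the plan has only a three-arm Kruskal-Wallis test between groups, which does not show whether PRO-087 is the arm that differs, as the safety rule requires.

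*Combined protocol and SAP*

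**What the plan says.** Section 8.3.1 names two tests for continuous quantitative variables. Within an arm it is "Intra-group analysis: Wilcoxon rank test"; between arms it is "Inter-group analysis: Kruskal-Wallis test". The Summary repeats the between-arm choice and words it more widely: "The statistical analysis will be carried out through the Kruskal-Wallis test for quantitative variables". The significance level is set once: "The level of difference to consider significance will be an alpha of 0.05 or less". Sections 8.3.1 to 8.3.3 contain no pairwise, post-hoc or PRO-087-specific contrast for these variables, and the partial analysis in 8.3.2 reuses the same methods.

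For qualitative variables the comparison "will be done by creating 2x2 contingency tables". For a binary variable such a table holds two arms at a time. Quantitative variables have no equivalent two-arm step.

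The decision rule in 8.3.1 calls the investigational drug "safe and tolerable when there are no clinical and statistical differences in all the variables of primary outcome, with respect to its comparators". The alternative hypothesis in 5.5.3 is that PRO-087 "presents a safety and tolerability profile similar to comparators in healthy subjects". Both statements are about PRO-087 against its comparators, and neither gives a direction.

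**The concern.** The rule and the test ask different questions. The rule asks whether PRO-087 differs from Xyel or from Systane. Kruskal-Wallis asks whether any of the three arms differ. One of the three pairwise gaps it responds to, Xyel against Systane, carries no information about PRO-087.

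The primary variables affected are those that Table 5 classes as continuous: goblet cell density, intraocular pressure and most laboratory values. Under the Summary's wider wording the eye comfort index, classed as discrete, is affected too.

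After a significant result the plan does not say how to decide whether PRO-087 is the arm that differs. Any pairwise follow-up would then be chosen by sponsor staff with the results in hand. The statement at stake is the trial's main conclusion, that PRO-087 is safe and tolerable.

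**Working it through.** The plan gives no operating figure for this analysis, so there is none to reproduce. Its sample size rests on an adverse-event proportion and does not bear on this point.

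**Inputs from the documents:** three arms allocated 1:1:1 (7.1), 10 subjects per arm (6.6.1), Kruskal-Wallis at alpha 0.05 (8.3.1).

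**Assumptions:** normal data, SD = 1, one value per subject, differences in SD units shown over a range.

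**1. Worked example.** Let the PRO-087 values be 0, 1, ..., 9. Shift one comparator down by 2.3 and the other up by 2.3. There are no ties. The rank sums are 98 (lower comparator), 155 (PRO-087) and 212 (upper comparator).

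- Kruskal-Wallis: H = 12/(30 x 31) x (98² + 155² + 212²)/10 - 3 x 31 = (12/930) x 7857.3 - 93 = 8.38. On 2 df, p = exp(-8.38/2) = 0.015.
- Mann-Whitney by normal approximation without continuity correction: the SD of U is sqrt(10 x 10 x 21/12) = 13.23.
- PRO-087 against either comparator: U = 72 or 28, z = 22/13.23 = 1.66, p = 0.096.
- Comparator against comparator: U = 15, z = 35/13.23 = 2.65, p = 0.008.

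The omnibus test is significant, neither PRO-087 contrast is, and the comparator gap drives the result.

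**2. How often this happens.** The event counted is Kruskal-Wallis p<=0.05 with neither PRO-087 contrast at p<=0.05 (two-sided). Simulations used 5,000 to 40,000 trials per scenario.

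| True position | Kruskal-Wallis significant | Significant, neither PRO-087 contrast at p<=0.05 |
|---|---|---|
| PRO-087 midway, comparators 0.5 SD apart | 13.2% | about 4% (3.5% in the largest run) |
| PRO-087 midway, 1.0 SD apart | 41.9% | 12.4% to 15% |
| PRO-087 midway, 1.5 SD apart | 77.6% | 17.9% |
| PRO-087 equals one comparator, other 1.0 SD away | 54.2% | 7.1% to 9% |

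The ranges mainly reflect the form of the Mann-Whitney p-value. At U = 24 the uncorrected normal approximation gives z = 26/13.23 = 1.97 and p just under 0.05, while the exact p is just over it. The exact test therefore leaves more trials with no significant PRO-087 contrast.

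If 20 eyes per arm were analysed as independent values (midway, 1.0 SD apart), the two columns would read 76.4% and 19.3%.

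**3. Effect of direct contrasts.** Take PRO-087 against each comparator, Mann-Whitney, two-sided 0.025 each. With no true difference the chance of any significant result is 4.3%, against 4.4% for Kruskal-Wallis, so the error rates match. With PRO-087 midway and comparators 0.5, 1.0 and 1.5 SD apart, a significant result falls from 13.2% to 8.2%, from 41.9% to 20.6%, and from 77.6% to 42.8%.

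**4. Power when PRO-087 is 1 SD worse than both comparators.** The two contrasts at 0.025 each give 58%, Kruskal-Wallis 55%: a gain of about 3 points.

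**The case against.** The strongest counter-argument is that the rule already limits the damage. It speaks of differences with respect to the comparators and asks for clinical as well as statistical differences. Group means, SDs and ranges will also be reported. Nowhere does the plan say that an omnibus p<=0.05 means failure, so a reader could set aside a result that came only from Xyel and Systane. The study is also labelled exploratory, with descriptive specific objectives. This stands in part: the plan permits such a judgement, and it is why the point is about what can happen. But no clinical difference is defined for the rule, and no step is provided for making the judgement.

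Two stronger readings are tempting and are not supported.

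- **A reader might infer that PRO-087 would fail in more than half of trials merely because one marketed product did worse.** When PRO-087 equals Xyel and Systane is 1 SD worse, Kruskal-Wallis is significant in about 54-55% of trials. But PRO-087 then truly differs from Systane, and a non-directional rule counts that as a difference. Two-sided contrasts are significant in 54.5% of trials at 0.05 each and in 42% at 0.025 each. Only a one-sided test for harm brings the figure down to about 2%, and the documents specify no such test.
- **A reader might infer that the omnibus test loses much power to detect harm from PRO-087.** A comparison of 69% with 55% can be produced, but it sets contrasts at one-sided 0.025 each, without an alpha split, against a non-directional test. At matched two-sided error the gap is about 3 points.

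**Conclusion.** The point holds as a mismatch between test and decision rule, and it should be fixed. For quantitative primary variables the only planned between-arm test cannot say whether PRO-087 is the arm that differs, and the Xyel-Systane gap can drive its result.

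Per variable, a significant omnibus result with neither PRO-087 contrast significant is expected in about 4% of trials (PRO-087 midway, comparators 0.5 SD apart), about 12-15% (midway, 1 SD apart) and about 7-9% (PRO-087 equal to one comparator, the other 1 SD away). These figures rest on normal data, 10 subjects per arm, one value per subject and assumed separations. Nothing in the documents indicates how far apart Xyel and Systane really are in healthy eyes. If they do not differ, the problem is small.

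**What to change.** In 8.3.1, for each quantitative primary variable:

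- Make PRO-087 versus Xyel and PRO-087 versus Systane the decision analysis, each by Mann-Whitney with a signed Hodges-Lehmann difference and confidence interval.
- State sidedness and alpha. One option is two-sided 0.025 each, with 97.5% intervals. Another is one-sided tests in a direction of harm fixed in advance for each variable; the non-directional wording of 5.5.3 and of the rule would then have to be aligned.
- State that a Xyel-Systane difference does not bear on the PRO-087 conclusion.
- Keep Kruskal-Wallis as a descriptive result, and do not use it as a gate for the contrasts.
- Make the same change in the Summary. Section 8.3.2 follows by reference.

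The cost is SAP wording and two tests per variable with a stated alpha split. No subjects, visits or measurements are added. The change repairs attribution only: a non-significant contrast would still not be evidence of similarity, and that needs separate treatment.

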#### 6.4.3 Methods and scales to be used for the measurement of the variables

Variable	Unity	Symbol	Туре	Method of measurement	Normal value
Age	Years		Continuous	Calculation from the date of birth	NA
Gender	Female Male	F / M	Nominal	Direct questioning	NA
Adverse events	Number of cases	n	Discreet	Count	NA
Intraocular pressure	Milimeters of mercury	mmHg	Continuous	Goldman's applanation tonometry	11 - 21
Visual ability	Fraction	Snellen	Nominal	Primer	
Tear rupture time	Seconds	S	Continuous	Direct count	> 10
Eye comfort index	points		Discreet	Questionnaire	
Adverse events	Present / Absent		Nominal	Comprehensive valuation	Absent
Goblet cell density	Cells per square millimeter	Cel/mm 	Continuous	Cytology by impression	> 500 cel/mm 
Vital signs					
Heart rate	Beats per minute	lpm	Discreet	Auscultation	60 - 100
Breathing frequency	Breaths per minute	rpm	Discreet	Auscultation	12 – 24
Systemic blood pressure	Milimeters of mercury	mmHg	Continuous	Non-invasive auscultatory measurement	< 120 / 80
Previous segment					
Epithelial defects	Degrees		Discreet	Direct observation with fluorescein and green lysamin stain	Oxford Scale

Sophia Laboratories, S.A. of C.V.

Variable	Unity	Symbol	Туре	Method of measurement	Normal value
Ophthalmologic signs ar	nd symptoms				
Conjunctival hyperemia	Normal / Very Light / Mild / Moderate / Severe		Ordinal	Direct observation. Classification of Efron.	Normal
Chemosis	Present / Absent		Nominal	Direct observation	Absent
Burning	Severity: Absent, very mild, mild, moderate and severe		Nominal	Direct questioning	Absent
Foreign body sensation	Severity: Absent, very mild, mild, moderate and severe		Nominal	Direct questioning	Absent
Pruritus	Frequency: At all times, almost at all times, 50% of the time, almost in no time, at any time		Nominal	Direct questioning	Absent
Postinstilation symptoms	5				
Burning	Present / Absent		Nominal	Journal of the subject	Absent
Foreign body sensation	Present / Absent		Nominal	Journal of the subject	Absent
Pruritus	Present / Absent		Nominal	Journal of the subject	Absent
Red eye (symptom)	Present / Away		Nominal	Journal of the subject	Absent

Sophia Laboratories, S.A. of C.V.

Variable	Unity	Symbol	Туре	Method of measurement	Normal value
Posterior segment					
Magula	Normal /				
Macula	Abnormal		Nominal	Observación directa	Normal
Optical disk integrity	Normal / Abnormal		Nominal	Observación directa	Normal
Blood count					
Erythrocytes		M/uL	Continuous		

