# 6.4.3.1 Visual ability.

Visual acuity (VA) is a test of visual function. Spatial visual acuity is the ability to distinguish separate elements of an object and identify them as a whole. It is quantified as the minimum separation angle (located at the nodal point of the eye) between two objects that allows perceiving them as separate objects.

Snellen's notation is described as the distance at which the test is performed, divided by the distance at which the letter is vertically equivalent to 5 arc minutes. Thus, at 6 meters a letter 6/6 (20/20) equals 5 minutes of arc, a letter 6/12 (20/40) equals 10 minutes, and a letter 6/60 (20/200) equals 50 minutes The Snellen fraction can also be expressed as a decimal (ie 20/20 = 1 and 20/40 = 0.5). [38]

The VA will be evaluated basally, without refractive correction with the Snellen chart. Which will be located in a place with adequate lighting, natural or artificial and at a distance of 3m from the subject to be evaluated. The visual acuity of each eye will be taken, starting with a right eye (DO) asking the subject to keep both eyes open and using an occluder to cover the left eye (OS); the subject will read aloud the lines that the evaluator points out, the line of smaller letters that he reaches to see will be annotated by the fractional evaluator as the DO of the DO in the clinical record. Proceed to the OS with the same method.

Subsequently the best refractive correction of the subject will be made and the examination will be repeated using the obtained refraction. This result will be reported as CV, it will be written in fraction in the clinical file and in the CRF, in addition in the CRF it will be written in decimal. By definition, the CV can not be inferior to the AV.

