#### 6.4.3.9 Ocular symptomatology.

The subject will be questioned directly about the presence in general (since the last visit) of the following symptoms: burning, foreign body sensation and pruritus. Respond about the severity and frequency of symptoms such as:

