#### Severity: Absent (0), very mild (1), mild (2), moderate (3) and severe (4)

Frequency: At all times (4), almost at all times (3), 50% of the time (2), almost at no time (1), at any time (0).

The number corresponding to each symptom will be registered in the CRF.

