#### Symptomatology postinstilación:

The subject will be requested, that in the subject's daily instrument, after registering the application of the product under investigation, mark YES or NO according to the presence of the following symptoms: burning, sensation of a foreign body, red eye and pruritus.

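### The 2x2 rule for qualitative variables cannot be run on five-level grades in three arms without a cut-point and arm pairing that the plan does not give, and use of baseline in the between-arm tests is not specified

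*Combined protocol and SAP*

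**What the plan says.** Section 8.3.1 states that significance testing of the qualitative variables, nominal and ordinal alike, "will be done by creating 2x2 contingency tables". McNemar is the within-arm test and Pearson chi-square the between-arm test. The Summary names chi-square for qualitative variables and sets no table size.

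Table 5 (section 6.4.3) grades conjunctival hyperaemia as "Normal / Very Light / Mild / Moderate / Severe" and types it ordinal. Burning and foreign body sensation have a five-level severity scale. Pruritus has "Frequency: At all times, almost at all times, 50% of the time, almost in no time, at any time". All three symptoms are typed nominal. Section 6.4.3.9 asks for both dimensions ("Respond about the severity and frequency of symptoms such as") and codes each from 0 to 4. After each instillation the subject must also "mark YES or NO according to the presence of the following symptoms" in the diary. Visual ability is typed nominal, although section 6.4.3.1 says of the result that "in addition in the CRF it will be written in decimal".

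Sections 6.6 and 7.1 give three arms of 10 subjects, allocated 1:1:1. For continuous variables section 8.3.1 names Wilcoxon within arm and Kruskal-Wallis between arms, with no response variable or covariate. Baseline is measured (sections 6.4.4 and 6.5). The specific objectives (5.5.2) speak of changes in intraocular pressure, stains, laboratory tests, visual capacity, break-up time and comfort index, but for goblet cells only of the density.

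**The concern.** A 2x2 table holds two categories and two groups. Five grades in three arms do not fit until someone decides where to cut the scale and which arms to compare. The plan leaves both choices to the analyst. It also leaves open whether severity, frequency or the diary answer is the tested form of each symptom.

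Most of these are primary safety or tolerability variables. Section 8.3.1 declares the product safe and tolerable when the primary variables show no clinical and statistical differences from the comparators. A cut with little power, or a less sensitive test, therefore makes the favourable conclusion easier to reach. Whether that decision rule is sound is a separate matter.

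The analysts are blinded (7.4, 8.3.1). But the arms carry number codes, so the p-value between codes can be seen at every cut. Blinding limits a choice of cut after the fact but does not rule it out.

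**Working it through.** The plan gives no power or cut-point for these tests, so it has no figure to reproduce.

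**Choices left open.** Five ordered levels allow 5 − 1 = 4 cuts. Three arms allow 3 pairings. That makes 4 × 3 = 12 different 2x2 tables per graded variable and visit, all consistent with the text. Chemosis and the diary items are already binary, so for them only the pairing is missing. On the Summary's wording, one unordered 3x5 table is a further reading.

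**Graded variables.** The documents give the number of arms (3), subjects per arm (10), levels (5) and alpha (0.05). The grade distributions are assumed. Two arms follow the first distribution and one arm the second; shares run from the lowest grade to the highest.

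- Near the floor: 80/12/5/2/1% against 45/25/15/10/5%.
- General shift: 40/35/15/7/3% against 20/20/25/20/15%.

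In each simulated trial (20,000 per scenario for the powers) the grades were tested by three-arm Kruskal-Wallis. They were also tested by Pearson chi-square, Σ(O − E)²/E on 2 degrees of freedom, in the 3x2 table at each cut, and by the 3x5 chi-square. Power:

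| Test | Near floor | General shift |
|---|---|---|
| Kruskal-Wallis, final grade | 40% | 33% |
| Cut at present/absent | 38% | 13% |
| Cut at mild or worse | 27% | 35% |
| Cut at moderate or worse | 11% | 29% |
| Cut at severe | 1% | 12% |
| Unordered 3x5 table | 16% | 17% |

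Present/absent and Kruskal-Wallis disagree on significance in about 6% of trials near the floor and 24% under the general shift. The two lowest cuts disagree with each other in about 27% and 31%.

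Pairing also matters. Near the floor at present/absent, one 3x2 table has 38% power and a single 2x2 table 34%. Two 2x2 tables against the worse arm give at least one significant result in 48%.

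**Using the baseline grade.** With baseline-to-final correlations of 0.3/0.5/0.7, power near the floor is:

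- Kruskal-Wallis on change: 31/37/47%.
- Kruskal-Wallis on the final grade: 40% at each.
- Rank ANCOVA on the baseline grade: 42/44/49%.

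Under the general shift, rank ANCOVA gives 36/40/50%, against 33–34% on the final grade.

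**Continuous variables.** With equal SDs and correlation r, the residual SD is 1 for the final value, √(2(1 − r)) for change and √(1 − r²) for ANCOVA. For two arms of 10 at 80% power, the detectable difference on the final value is √(2/10) × (1.96 + 0.84) = 1.25 SD. At r = 0.3/0.5/0.7:

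- Change: 1.25 × √(2(1 − r)) = 1.48/1.25/0.97 SD.
- ANCOVA: 1.25 × √(1 − r²) = 1.20/1.09/0.89 SD.

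So change beats the final value only when r exceeds 0.5, while ANCOVA is never worse in this approximation. Simulated power for three arms of 10, one shifted by 1 SD, agrees:

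| Method | r = 0.3 | r = 0.5 | r = 0.7 |
|---|---|---|---|
| Kruskal-Wallis, final value | 54% | 54% | 54% |
| Kruskal-Wallis, change | 41% | 54% | 78% |
| ANCOVA | 61% | 69% | 86% |
| Rank ANCOVA | 58% | 66% | 81% |

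**The case against.** The best defence is that present/absent is the natural reading. Table 5 lists Normal or Absent as the normal value, McNemar is a test for paired binary data, and in healthy subjects most grades will sit at the floor, where that cut loses only 2 points of power. One sentence stating the cut and the comparison would make the rule executable. This stands as to size near the floor. But no passage makes the normal value an analysis rule, and under a general shift the same cut is weak.

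Nor is any one test best everywhere. If the worse arm has the same share of symptomatic subjects but many severe ones (30/40/20/8/2% against 30/5/10/25/30%), the moderate-or-worse cut has 68% power and Kruskal-Wallis 30%. The case for an ordered analysis is that it needs no cut, not that it always wins.

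A reader might infer that the plan ignores baseline. The documents do not support that. The within-arm tests use it, and section 8.3.1 does not say whether Kruskal-Wallis runs on the final value or on change. The objectives' wording points to change for several variables. The fair statement is that use of baseline is not specified. Kruskal-Wallis on the final value would also be valid under randomisation.

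A reader might also ask how often all four cuts agree, and find disagreement in 48–50% of trials. That figure is inflated by cuts with almost no power, so the comparisons under working are the fairer measure.

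**Conclusion.** The 2x2 rule is wrong as written: it cannot be applied to four graded variables in three arms without choices that the plan does not make. It is also not stated which symptom score is tested, and typing visual ability as nominal sends a measure recorded as a decimal to the same tables.

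The loss is small if present/absent is fixed in advance and grades stay near the floor. It is substantial if grades shift more generally or a higher cut is used.

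On baseline, the plan is silent rather than wrong. Specifying ANCOVA is a cheap improvement, worth 7 to 32 points of power in the case shown (61 − 54 and 86 − 54). Change from baseline alone is not reliably better than the final value.

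The sizes rest on assumed distributions, correlations and a 1 SD shift, with 10 analysed subjects per arm and one value per subject. That unit fits the visit symptoms if they are answered once per subject, which section 6.4.3.9 suggests but does not state. For eye-level grades it is not the plan's 60 eyes. The direction does not depend on these figures: an undefined cut or a less sensitive test favours a finding of no difference.

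**What to change.** 1. Delete the 2x2 limit. Analyse Efron, Oxford and visit symptom grades as ordered scores, one value per subject, in one three-arm comparison at the final visit. Use rank ANCOVA on the baseline grade, with Kruskal-Wallis on the final grade as the check and Wilcoxon signed-rank within arm. Name the tested score for each symptom, for example as Table 5 lists them, and treat the other score and the diary as supportive.
2. For goblet cell density, intraocular pressure, comfort index and break-up time, use ANCOVA on baseline with a three-level arm term and one value per subject (mean of both eyes for eye-level measures). Report PRO-087 minus each comparator with 95% confidence intervals, with rank ANCOVA as the check. Use rank ANCOVA for decimal visual capacity and for laboratory values with adequate spread. Only describe near-constant differential counts, where a linear model is unsuitable.
3. For truly binary variables, use a 3x2 table by subject with Pearson chi-square, plus risk differences with 95% confidence intervals.
4. Keep days 3 and 6 descriptive.
5. Correct the Table 5 types: visit symptoms and Oxford grades ordinal, visual ability quantitative.

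The cost is wording in section 8.3.1 and Table 5 and slightly more analysis work, with no new data. ANCOVA adds a linearity assumption, which the rank version checks. The subject replaces the eye as the unit; both eyes receive the same product, and these tests assume independent values.
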